9.7. Warnings and Precautions

Special warnings or precautions for the study drug, derived from safety information collected by the sponsor or its designee, are presented in the [IB](#). Additional safety information collected between IB updates will be communicated in the form of Investigator Notifications. Any important new safety information should be discussed with the participant during the study, as necessary. If new significant risks are identified, they will be added to the ICF.

9.8. Product Complaints

The sponsor collects product complaints on study drugs and drug delivery systems used in clinical studies in order to ensure the safety of study participants, monitor quality, and facilitate process and product improvements.

All product complaints associated with material packaged, labeled, and released by the sponsor or its designee will be reported to the sponsor. All product complaints associated with other study material will be reported directly to the respective manufacturer.

The investigator or his/her designee is responsible for reporting a complete description of the product complaint via email or other written communication to the sponsor contact or respective manufacturer as noted in the packaging information. Any AE associated with a product complaint should be recorded as described in Section 9.3.

If the investigator is asked to return the product for investigation, he/she will return a copy of the product complaint communication with the product.

10. STATISTICS

10.1. Sample Size Determination

Overall, the study plans to enroll approximately 50 participants. Assuming ORR is 30%, 50 participants will provide at least 80% power to test the null hypothesis of $ORR \leq 15\%$ using a normal-approximate z test at 1-sided significance level of 0.05.

When a tumor subtype j within each cohort reaches 10 participants (or more), a statistical evaluation for ORR (p_j) within the subtype will be conducted. The tumor subtype j may be discontinued from further enrollment if the posterior probability $P(p_j < 0.15|n_j, N_j, \alpha, \beta) > 0.3$ where n_j is the number of responders in j th subtype, N_j is the number of participants with j th tumor subtype, α and β are parameters of the prior distribution and are set to be $\alpha = 1.7625$ and $\beta = 9.9875$ (Beta distribution with mean = 0.15, variance = 0.01). Tumor subtypes with at least 10 patients and $P(p_j < 0.15|n_j, N_j, \alpha, \beta) \leq 0.3$ may continue to enroll participants. Any tumor subtype j with at least 10 participants and $P(p_j > 0.30|n_j, N_j, \alpha, \beta) > 0.5$ may enroll up to 30 additional participants as an expansion cohort of the tumor subtype. These participants will not be counted towards the 50 participants planned for the study. At the end of the study, $P(p_j < 0.15|n_j, N_j, \alpha, \beta)$ and $P(p_j > 0.30|n_j, N_j, \alpha, \beta)$ will be evaluated for all tumor subtypes within each cohort (see [Table 14](#) and [Table 15](#)). A cohort of at least 25 participants will provide > 0.8 probability of observing 6 responders if underlying response rate is 0.3. The initial calculation of these posterior probabilities of each tumor subtype will begin when 10 participants have completed the assessment for primary response.

These rules based on posterior probabilities are provided as guidance for recruiting participants and discontinuing recruitment due to lack of response. The decision to continue recruiting to a tumor subtype or discontinue recruitment will be made based on the degree of responses observed (eg, number of CRs), other relevant clinical parameters, and medical assessments.

In addition to the aforementioned process, other methods including but not limited to hierarchical Bayesian models may be used to decide if a tumor subtype in each cohort will discontinue enrollment or continue to enroll subjects.

Table 14: $P(p < 0.15 | n/N, \alpha = 1.7625, \beta = 9.9875)$

Number of Responders	Number of Participants						
	N = 4	N = 5	N = 6	N = 7	N = 8	N = 9	N = 10
0	0.7384	0.7693	0.7969	0.8215	0.8433	0.8626	0.8797
1	0.4501	0.4933	0.5347	0.5740	0.6112	0.6460	0.6785
2	0.2108	0.2467	0.2837	0.3213	0.3592	0.3970	0.4344
3	0.0763	0.0965	0.1190	0.1437	0.1703	0.1987	0.2284
4	0.0215	0.0297	0.0397	0.0516	0.0654	0.0812	0.0988
5		0.0073	0.0106	0.0150	0.0205	0.0272	0.0353
6			0.0023	0.0035	0.0053	0.0075	0.0105
7				0.0007	0.0011	0.0017	0.0026
8					0.0002	0.0003	0.0005
9						0.0001	0.0001
10							0.0000

Table 15: $P(p > 0.3 | n/N, \alpha = 1.7625, \beta = 9.9875)$

Number of Responders	Number of Participants						
	N = 4	N = 5	N = 6	N = 7	N = 8	N = 9	N = 10
0	0.0258	0.0188	0.0137	0.0100	0.0073	0.0053	0.0038
1	0.1044	0.0808	0.0622	0.0477	0.0364	0.0276	0.0209
2	0.2627	0.2152	0.1749	0.1411	0.1131	0.0901	0.0713
3	0.4790	0.4141	0.3544	0.3006	0.2527	0.2108	0.1746
4	0.6928	0.6286	0.5643	0.5013	0.4411	0.3846	0.3325
5		0.8040	0.7514	0.6952	0.6371	0.5783	0.5202
6			0.8816	0.8426	0.7984	0.7500	0.6985
7				0.9319	0.9051	0.8731	0.8362
8					0.9625	0.9453	0.9236
9						0.9801	0.9696
10							0.9898

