3. OBJECTIVES AND ENDPOINTS

Table 7 presents the objectives and endpoints.

Table 7: Objectives and Endpoints

Objectives	Endpoints
Primary	
To determine the efficacy of pemigatinib in participants with locally advanced/metastatic or surgically unresectable solid tumor malignancies with an activating FGFR mutation or translocation	
• ORR: defined as the proportion of participants in each cohort who achieve a CR or PR based on RECIST v1.1
Secondary	
• PFS: defined as the time from first dose until PD (per RECIST v1.1 or RANO) or death (whichever is first) in each cohort• DOR: defined as the time from the date of first assessment of CR or PR until the date of the first PD (per RECIST v1.1 or RANO) or death (whichever is first) in each cohort• DCR: defined as the proportion of participants who achieved best overall response of CR, PR, or SD per RECIST v1.1 or RANO• OS: defined as the time from first dose of study drug to death of any cause in each cohort• Safety and tolerability: Occurrence of TEAEs and treatment-related AEs according to NCI CTCAE v5.0, physical exam changes, vital sign changes, laboratory evaluations, and ECG values in each cohort

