10.3. Level of Significance

The overall level of significance is 1-sided 0.05.

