10.4. Statistical Analyses

10.4.1. Primary Analysis

The primary endpoint of the study is ORR. Objective response rate is defined as the proportion of participants who achieved a CR or a PR based on RECIST v1.1 or RANO, as assessed by local radiological review. This analysis will be based on the efficacy evaluation population. Participants who do not have sufficient baseline or on-study response assessment information to be adequately assessed for response status will be included in the denominators in the calculation of ORR. The 90% CI for the ORR will be estimated using the Clopper-Pearson method. The p-value from the exact binomial test will be provided.

The ORR will also be analyzed based on the per protocol population as a sensitivity analysis.

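### Section 10.1 claims at least 80% power from a z test, but the exact binomial test named for the primary analysis has 77.7% power at 50 participants

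*Protocol*

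**What the plan says.** Section 10.1 of the protocol sets the overall size: "Overall, the study plans to enroll approximately 50 participants". It then gives the justification, for an assumed response rate of 30%: "50 participants will provide at least 80% power to test the null hypothesis of" a response rate of at most 15%, "using a normal-approximate z test at 1-sided significance level of 0.05".

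Section 10.3 fixes the error rate: "The overall level of significance is 1-sided 0.05".

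Section 10.4.1, on the primary analysis, names a different method. For the interval: "The 90% CI for the ORR will be estimated using the Clopper-Pearson method". For the test: "The p-value from the exact binomial test will be provided". It mentions no z test.

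The objectives table in section 3 has the primary endpoint as "ORR: defined as the proportion of participants in each cohort who achieve a CR or PR based on RECIST v1.1", which is by cohort, whereas the power sentence in 10.1 treats the 50 as a single group.

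**The concern.** The trial is sized with one test and analysed with another. With a binary endpoint and about 50 participants the two are not interchangeable. The exact test can reject only at whole responder counts whose tail probability is at or below 5%, so its actual type I error usually lies below 5% and its power falls with it. The z test ignores this.

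A reader of 10.1 will take 80% as the minimum chance that the primary analysis succeeds if the true response rate is 30%. If the exact test gives less, that reading is wrong. The reader is also not told how many responders are needed, and the two tests disagree at a plausible result, 12 responders out of 50.

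**Working it through.** **Inputs.** n = 50 pooled, null rate p0 = 0.15, alternative p1 = 0.30 (10.1); 1-sided alpha 0.05 (10.1 and 10.3); exact binomial test and 90% Clopper-Pearson interval (10.4.1). Participants who cannot be assessed stay in the denominator (10.4.1) and none are replaced (5.5), so n is not reduced.

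**Step 1: reproduce the figure in 10.1 (z test).**
- Critical proportion: p0 + 1.645 × √(p0(1 − p0)/n) = 0.15 + 1.645 × √(0.1275/50) = 0.15 + 1.645 × 0.0505 = 0.2331.
- Power: Φ((0.30 − 0.2331)/√(0.21/50)) = Φ(0.0669/0.0648) = Φ(1.033) = 84.9%.
- With continuity correction 1/(2n) = 0.01: Φ((0.0669 − 0.01)/0.0648) = Φ(0.879) = 81.0%.

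Both exceed 80%, so the claim is correct for the test it names.

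**Step 2: rejection rule of the exact test.** Find the smallest r with P(X ≥ r | n = 50, p = 0.15) ≤ 0.05.
- P(X ≥ 12) = 0.0628, too large.
- P(X ≥ 13) = 0.0301, acceptable.

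The exact test rejects at 13 or more responders (26%), with an actual type I error of 3.0%. The Clopper-Pearson limits agree: at 12/50 the 90% interval is 14.5% to 36.0%, which includes 15%; at 13/50 it is 16.1% to 38.1%, which does not.

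**Step 3: power of the exact test.** P(X ≥ 13 | n = 50, p = 0.30) = 0.7771, that is 77.7%. This is 80 − 77.7 = 2.3 points below the stated minimum and 84.9 − 77.7 = 7.2 points below the z-test figure. The true rate at which P(X ≥ 13 | 50, p) reaches 80% is 30.5%.

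**Step 4: where the tests disagree.** At 12/50 the uncorrected z statistic is (0.24 − 0.15)/0.0505 = 1.78, above 1.645, so the z test rejects. The exact p-value is 0.063, so the exact test does not. Using the z cut-off of 12 would give 86.1% power, but with a true type I error of 6.3%, above the level in 10.3.

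**Step 5: sensitivity to the exact number analysed.**

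| n | Responders needed | Actual alpha | Exact power at 30% |
|---|---|---|---|
| 47 | 12 | 0.0413 | 79.4% |
| 48 | 12 | 0.0478 | 81.9% |
| 49 | 13 | 0.0257 | 75.0% |
| 50 | 13 | 0.0301 | 77.7% |
| 51 | 13 | 0.0350 | 80.2% |
| 52 | 13 | 0.0404 | 82.5% |
| 53 | 13 | 0.0465 | 84.6% |
| 54 | 14 | 0.0256 | 78.6% |
| 55 | 14 | 0.0297 | 81.0% |

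Over n = 30 to 199, the largest size with exact power below 80% is 54.

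**The case against.** The strongest reply is that nothing in 10.1 is false: it names its test, and for that test the figure is right. That is true, but the power statement is there to describe the primary analysis, and the only test the protocol names for that analysis does not reach the stated minimum at the stated size.

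A second reply is that 10.4.1 says only that the exact p-value will be reported, and does not say that it decides success at 0.05. That is fair as to the letter. The reading is nevertheless the natural one: 10.3 sets 1-sided 0.05, and a 90% Clopper-Pearson interval is the exact interval matching a test at that level.

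A third is that enrolment is only approximate and a single further participant lifts power to 80.2%. This stands, and it is why the point is modest. It does not rescue the claim, because 49, 50 and 54 participants all fall short.

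A fourth is that the expansion participants allowed by 10.1 could raise the number analysed, since 10.2 defines the efficacy population as all enrolled and dosed participants. Section 10.1 says that those participants do not count towards the 50, and its power claim is made for 50.

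Last, pooling is an assumption. It is the assumption 10.1 itself makes, and it favours the plan: a single cohort of 25, taken as an illustration, would need 8 responders and have 48.8% power.

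**Conclusion.** The concern holds. At 50 pooled participants the exact binomial test at 1-sided 0.05 has 77.7% power at a response rate of 30%, against a stated minimum of 80%. The shortfall is 2.3 points.

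This rests on three readings: the 50 are pooled, as in 10.1; the exact p-value is judged at the level in 10.3; and the analysed number is exactly 50. The first two follow the protocol's own text or its plain sense. The third matters because power rises and falls from one sample size to the next.

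The consequence is a misstated power figure and an unstated responder threshold. The validity of the final p-value and interval is not affected; the exact test is the more conservative of the two.

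**What to change.** Restate the power sentence in 10.1 for the test named in 10.4.1 and remove the z test. For example: *With 50 participants, the exact 1-sided binomial test at 0.05 rejects a response rate of 15% or less when 13 or more respond (actual alpha 0.030), and has about 78% power if the true rate is 30%; for 48 to 53 participants, power ranges from 75% to 85%.*

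The wording should say that it refers to the pooled 50, so that it is not read as applying to each cohort.

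The cost is wording in 10.1 only. Sample size, analysis population, endpoint and test are unchanged. The stated power falls from at least 80% to about 78% at 50 participants. If the sponsor prefers to keep the 80% minimum, the table in the working shows which sizes near 50 meet it under the exact test; that would be a change to the sample size and not just to the text.

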2.1.2. Solid Tumor Malignancies With Activating FGFR Mutations and Translocations

Activation of the FGFR pathway by mutation or rearrangement is well recognized as an oncogenic event in cancer. A recent survey of 4853 solid tumors identified FGFR1-3 mutations or rearrangements in 2.25% of all tumors tested ([Helsten et al 2016](#)). Analysis of FGFR1-3 mutations and rearrangements in the NCI Genomic Data Commons Data Portal ([2019](#)), demonstrate that FGFR alterations are not restricted to 1 tumor type but rather broadly distributed across a diverse range of tumors (see [Table 5](#)). Importantly, preclinical and clinical data support the use of FGFR inhibitors in FGFR altered cell lines and tumors derived from a variety of cancer types, including bladder cancer, cholangiocarcinoma, endometrial cancer, glioma, and squamous lung cancer ([Porta et al 2017](#)).

Table 5: Tumors With Frequency > 1% for FGFR1-3 Mutations and Rearrangements in TCGA

Tumor Type	FGFR1		FGFR2		FGFR3		Total (%)
	Mutation (%)	Fusion (%)	Mutation (%)	Fusion (%)	Mutation (%)	Fusion (%)	
Urothelial carcinoma	0	0	0.75	0	12.64	3.15	16.54
Cholangiocarcinoma	0	0	0	13.9	0	0	13.9
Endometrial carcinoma	0	0	9.68	0.18	0	0	9.86
Glioblastoma multiforme	0.48	0	0	0	0.48	8.62	9.58
Lung squamous cell carcinoma	0.21	0.2	1.45	0.2	1.45	1.4	4.91
Cervical carcinoma	0	0	0.51	0	0	1.97	2.48
Renal papillary cell carcinoma	0	0	0	0	1.41	0.68	2.09
Rectal adenocarcinoma	0	0	2.01	0	0	0	2.01
Head and neck squamous cell carcinoma	0	0	0	0	1.14	0.76	1.9
Low grade glioma	0.19	0	0	0	0	1.71	1.9
Uterine carcinosarcoma	0	0	1.75	0	0	0	1.75
Esophageal adenocarcinoma	0	0.54	0	0	0	1.08	1.62
Stomach adenocarcinoma	0.25	0	0.5	0.48	0.25	0	1.48
Prostate adenocarcinoma	0	0	0	1.2	0	0.2	1.4
Breast (invasive) carcinoma	0	0.36	0.6	0.36	0	0	1.32
Adrenocortical carcinoma	0	0	1.1	0	0	0	1.1
Pheochromocytoma and paraganglioma	1.09	0	0	0	0	0	1.09
Colorectal adenocarcinoma	0.27	0	0.54	0	0.27	0	1.08
Skin cutaneous melanoma	0.21	0	0.84	0	0	0	1.05

Based on these observations, an FGFR inhibitor may be active across a variety of tumor types with activating point mutations and gene fusions of FGFR1-3.

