10.2. Populations for Analysis

Populations for analysis are shown in **Table 16**.

Table 16: Populations for Analysis

Population	Description
Efficacy evaluable	
The efficacy evaluable population includes all enrolled participants who received at least 1 dose of study drug.
 
The efficacy evaluable population will be used for the summary of demographics, baseline characteristics, participant disposition, and analyses of all efficacy data.

Safety	The safety population includes all enrolled participants who received at least 1 dose of study drug. All safety analyses will be conducted using the safety population.
Per protocol	The per protocol population includes all efficacy evaluable population participants who are sufficiently compliant with the protocol.

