10.5. Interim Analysis

No formal interim analysis is planned. However, each tumor subtype within each cohort will be assessed when 10 or more participants are enrolled.

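### Expansion participants are outside the 50 that the study is powered on, but as written inside the primary ORR test; the primary test set must be stated

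*Protocol*

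**What the plan says.** - **Sizing (Protocol 10.1).** About 50 participants give at least 80% power for an ORR of 30% against a null of at most 15%, by a z test at one-sided 0.05.
- **Expansion (10.1).** A tumor subtype with at least 10 participants and a posterior probability above 0.5 that its ORR exceeds 30% "may enroll up to 30 additional participants as an expansion cohort of the tumor subtype". The next sentence reads: "These participants will not be counted towards the 50 participants planned for the study".
- **Analysis set (10.2, Table 16).** "The efficacy evaluable population includes all enrolled participants who received at least 1 dose of study drug". The set serves "participant disposition, and analyses of all efficacy data". Expansion participants are not set apart.
- **Primary analysis (10.4.1).** ORR with a 90% Clopper-Pearson CI and an exact binomial p-value: "This analysis will be based on the efficacy evaluation population".
- **Unit of the endpoint (Tables 1 and 7).** ORR is the "proportion of participants in each cohort who achieve a CR or PR based on RECIST v1.1". Sections 10.1 and 10.4.1 do not repeat the per-cohort qualifier for ORR.
- **Timing of the subtype look.** Section 10.5 says "each tumor subtype within each cohort will be assessed when 10 or more participants are enrolled". Section 10.1 starts the calculation once 10 participants have had their primary response assessed.

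**The concern.** The sample size section and the analysis sections describe different sets. One is a planned 50 that excludes the expansion. The other is everyone dosed, which includes it. Nothing in the protocol reconciles them.

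Expansion participants do not enter at random with respect to outcome. They are recruited because their subtype has responded. If they join the primary test, the denominator becomes 50, 80, 110 or more depending on observed responses, and the tested average shifts toward the subtype that did well. The study could then reject an ORR of at most 15% although the mix it set out to accrue has an ORR of 15%. The power statement would also no longer describe the test that is run. This arises when one subtype responds and the others do not, which is the situation the expansion rule serves.

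The unit of the test is a related gap: one pooled test, or one per cohort.

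**Working it through.** **1. The plan's own power.** With n = 50, p0 = 0.15, p1 = 0.30 and z = 1.645:
Φ[(√50 × 0.15 − 1.645 × √(0.15 × 0.85)) / √(0.30 × 0.70)] = Φ[(1.0607 − 0.5873) / 0.4583] = Φ(1.033) = 0.849. The stated figure of at least 80% is reproduced, for one pooled test of 50. For a cohort of 25: Φ[(0.75 − 0.5873) / 0.4583] = Φ(0.355) = 0.64.

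**2. Exact test.** The critical values are 13/50 (size 0.030) and 18/80 (size 0.048).

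**3. Expansion trigger.** The posterior is Beta(1.7625 + n, 9.9875 + N − n). Table 15 gives 0.5202 for 5/10 (expand) and 0.3325 for 4/10 (do not). The chance of at least 5 of 10 is 0.01 at an ORR of 15%, 0.15 at 30% and 0.50 at 45%.

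**4. Range of the denominator as written.** At most five subtype cells can each hold 10 of the 50, so it runs from 50 to 50 + 5 × 30 = 200.

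**5. Simplest case, exact enumeration.** Assume that one subtype holds 10 of the 50, has one look, and adds 30 if at least 5 of 10 respond.
- All subtypes at 15%: rejection is 3.0% on the 50 and 3.0% with the expansion. No inflation.
- That subtype at 30%, the others at 11.25%: the mean over the 50 is (10 × 0.30 + 40 × 0.1125)/50 = 0.15. Over 80 it is (40 × 0.30 + 40 × 0.1125)/80 = 0.206. Rejection goes from 2.7% to 10.9%.
- That subtype at 40%, the others at 8.75%: the mean over 80 is 0.244. Rejection goes from 2.2% to 31.9%.

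**6. Accrual weighted by Table 5.** The protocol gives no accrual mix. As an assumption, take the table headed "Tumors With Frequency > 1% for FGFR1-3 Mutations and Rearrangements in TCGA" without its urothelial and cholangiocarcinoma rows, since the protocol excludes bladder cancer and cholangiocarcinoma. The 17 remaining rows total 46.62. Endometrial mutations are 9.68/46.62 = 20.8%, or 10.4 of 50 expected. Glioblastoma fusions are 8.62/46.62 = 18.5%. The other cells are set so that the accrued mix stays at 15%. Simulation: random accrual to 50, rule checked from N = 10 onward, later participants of the subtype kept in the 50, exact test at the realised n.

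| Cell and its ORR | Runs with an expansion | Rejection, planned 50 | Rejection, plus 30 |
|---|---|---|---|
| Endometrial mutation, 30% | 11% | 3% | 9% |
| same, 36% | 19–20% | 3% | 16–17% |
| same, 45% | 34% | 3% | 33% |
| Glioblastoma fusion, 30% | 8% | 3% | 7% |
| same, 36% | 14% | 3% | 13% |
| same, 45% | 25% | 3% | 24% |

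**7. Sensitivity.**
- Only 10 added to the 20.8% cell: 5%, 7–8% and 14% at ORR 30%, 36% and 45%.
- Cell at 15% of accrual, 30 added: 7–8% at ORR 36% and 12% at 45%.
- Cell at 10% of accrual, 30 added: about 4%.
- Eight or 17 equal-sized types split evenly over the cohorts, one type at 45%: 3%, no visible effect.

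**8. What it can look like in data.** 8/50 gives exact p = 0.48 and a 90% CI of 8.2–27.0%. Adding 12/30 from one expansion gives 20/80, p = 0.013 and a 90% CI of 17.2–34.2%.

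**The case against.** **The exclusion from the 50 may be recruitment accounting only.** The sentence stands among enrollment rules, and Table 16 can be read as applying its definition consistently. This stands so far as intent goes: the documents do not show which set is meant. But on that reading the primary test does pool participants recruited because of response, and on the other reading Table 16 is wrong. One statement is needed either way. It is not a detail for the statistical analysis plan, because the protocol itself fixes the sizing, the population and the test.

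**This is not type I error inflation in the usual sense.** A reader might infer that the trial's false-positive rate is generally raised. The documents do not support that: with a common ORR, or with no expansion, rejection stays at 3%. The higher figures take the null to be a 15% ORR in the accrued mix, and in each of them one subtype truly responds. It is a question of which average is tested.

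**The magnitudes lean high.** This stands too. Section 4.1 allows tumor types to be capped so that no single type drives the analysis. Cohort B excludes kinase-domain mutations, which Table 5 does not separate out. Primary brain tumors with prior bevacizumab are excluded. The expansion is optional, of up to 30, under rules that 10.1 calls guidance. Each could shrink the dominant cell or the number added.

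**Restricting the test to the 50 is incomplete by itself.** Section 10.1 does not say where later participants of a qualified subtype go. If they are diverted to the expansion, the 50 loses the responding subtype, and rejection on the 50 falls to about 1% with the cell at 45%. The fix therefore needs an allocation rule.

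**Two further inferences go too far.** The per-cohort wording does not show that a per-cohort test with 64% power is planned, since the power statement fits only a pooled test. Nor does the wording of 10.5 show that unassessed participants will count as non-responders, since 10.1 says when the calculation begins.

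**Conclusion.** The point holds as an unresolved inconsistency about the primary test set and should be fixed. Followed as written, the plan gives a primary ORR, CI and exact test whose denominator and case mix depend on outcome, while the stated power refers to a fixed 50.

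The size is conditional. Rejection of an ORR of at most 15% rises from about 3% to 7–33% if one cell takes about 18–21% of accrual without a cap, has an ORR of 30–45% within an accrued mix of 15%, and adds the full 30. It is about 5–14% if the 20.8% cell adds only 10, and about 4% for a cell at 10% of accrual. It disappears if no subtype expands or all share one ORR. The protocol gives neither an accrual mix nor subtype ORRs, so these figures illustrate the mechanism and do not predict the result. The textual conflict does not depend on them. The pooled-or-per-cohort question is a real but secondary ambiguity, and the 10.5 wording is minor.

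**What to change.** 1. In Table 16 and 10.4.1, state that the primary ORR test and its 90% CI use only participants enrolled toward the planned 50.
2. In 10.1, state in advance whether participants of a subtype that has qualified for expansion, enrolled before the 50 are complete, fill the 50 or the expansion.
3. Report expansion participants separately by subtype with 90% CIs.
4. State that the 15% test is the pooled test that 10.1 powers, and align Tables 1 and 7 by giving the per-cohort ORR as an estimate with its CI.
5. Minor: word the trigger in 10.5 as in 10.1, on participants with a completed response assessment. With imaging every 9 weeks, that look comes about 9 weeks after the tenth enrollment, and at least 4 weeks later if response must be confirmed.

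**Cost.** Wording only, with no added participants or procedures. Expansion data then add no precision to the primary estimate. Mix shift from futility closure or caps remains. With closure simulated at 2 or fewer responders of 10, rejection on the 50 alone stays at about 3% in the Table 5 mix. It reaches 21% in an extreme of four equal types, each wholly in one cohort, with one at 45%.
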